### 9.5 Efficacy analyses

### 9.5.1 Primary Variable

The PaO2/FiO2 ratio will be analyzed at two time points: 0 hours (time of ICU admission) and 24 hours after ICU admission. These analyses will be performed using both the ITT and PP populations with the ITT analysis considered as the primary result. As this is not a pivotal study and the contrast estimates will be obtained from a repeated measurements model fitted for data at both time points, adjustments for multiplicity are not considered necessary.

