4.2. STUDY ENDPOINTS

4.2.1. Efficacy endpoints

4.2.1.1. Primary efficacy endpoint

- PaO₂/FiO₂ ratio measured at FiO₂ = 1 during mechanical ventilation on ICU admission (time 0) and at 24 hours after ICU admission. Patients on FiO₂ < 1 will be turned back to FiO₂ = 1 for 5 minutes before gas measurement.

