9. STATISTICAL ISSUES

9.1. SAMPLE SIZE

The sample size has been estimated based on PaO₂/FiO₂ ratios immediately and at 24 hours from the results of 700 lung transplant operations at the Washington University. The database reports means and standard deviations for this endpoint of 329±137 mmHg at the initial ICU assessment and 315±117 mmHg at 24 hours.

A sample size of 50 in each group will have a 81% power to detect a difference in means of 70 mmHg (the difference between a placebo mean of 315 and a treated mean of 385, a 22% improvement) assuming that the common standard deviation is 137 using a two group t-test with a 0.05 one-sided significance level. Alternatively, a sample size of 50 in each group will have a 56% power to detect a difference in means of 50 mmHg (the difference between a placebo mean of 315 and a treated mean of 365, a 15% improvement) assuming that the common standard deviation is 137 using a two group t-test with a 0.05 one-sided significance level.

There is no currently available data to provide a knowledgeable estimate of the effect size in this study. If the effect size is smaller than 15%, the power of this study will be reduced and the chance of a Type II error is increased. Under such circumstances, this study would still provide valuable data regarding the effect size in the primary outcome variable as well as the results in all of the secondary, exploratory endpoints and subgroup analysis.

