9.4.2. Primary efficacy analysis

The PaO₂/FiO₂ ratio will be analyzed separately, at the two time points: 0 hours (ICU admission) and 24 hours after ICU admission. Analysis of variance will be used, including terms for treatment and center. The importance of the treatment by center interaction will be investigated but if this is not significant at the 10% level, this term will be excluded from the final model. If a center by treatment interaction is detected, alternative methods of presentation will be explored. Treatment effect will be primarily compared using a one-sided 0.05 level test and then re-tested for consistency with a two-sided 0.05 level test. Type of transplant (single or bilateral) will then be included in the model of the analysis to explore any possible, even unanticipated, differences due to the specific procedure.

Primarily the data will be analyzed excluding missing data. As confirmatory analysis, the ANOVAs will be performed substituting any missing values by the last observation carried forward (LOCF) method, in patients extubated before 24 hours. If the data are missing due to

patient death, the PaO₂/FiO₂ ratio will be given a zero value. If the data are missing due to lack of recording while on mechanical ventilation, these data will not be substituted.

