### 3.2 Sample Size Considerations

Under the following assumptions:

1. A single primary endpoint –  $\text{PaO}_2/\text{FiO}_2$  ratio
2. One primary comparison: repertaxin versus placebo at 24 hours post ICU admission ( $H_0: \mu_R = \mu_P$ ;  $H_1: \mu_R > \mu_P$ ).
3. A one-sided two group t-test of statistical significance
4.  $\alpha$ -level or probability of Type I error associated with the test of 0.05
5. A placebo mean of 315 mmHg
6. A common standard deviation of 137 mmHg
7. A sample size of 50 in each group

the study has 81% power to detect a difference in means of 70 mmHg ( $\mu_R = 385$  mmHg) and 56% power to detect a difference in means of 50 mmHg ( $\mu_R = 365$  mmHg). The data for assumptions 5 and 6 is taken from the results of 700 lung transplant operations at the Washington University. However, there are currently no data available to provide an estimate of the treatment effect size for this study.

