## 4 STUDY VARIABLES AND COVARIATES

### 4.1 Primary variable

The primary variable within the study is  $\text{PaO}_2/\text{FiO}_2$  ratio measured at ICU admission (time 0) and 24 hours post ICU admission.

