#### Primary analysis

The ratio at the two time points will be analyzed using a repeated measurements model using PROC MIXED within SAS®. The model will include fixed effect terms for center, time point and treatment. Time point will be specified as a repeated measurement. In order to select an appropriate matrix for the observations within each patient, 3 models will be fitted using the compound symmetry, Huynh-Feldt and unstructured structures. The matrix for the final model will be selected using Akaike's Information Criterion where the lowest value indicates the best fit. Type III sums of squares from the mixed procedure within SAS® will be used to assess the significance of individual terms within the model using the selected matrix structure. The importance of the treatment-by-center interaction will be investigated but if the term is not significant at the 10% level, it will be excluded from subsequent models. If there are insufficient data within each center and treatment combination to allow estimation of effects, centers will be pooled based on similar surgical practices.

The adjusted least squares means will be estimated for each combination of time point and treatment. The treatment effect within each time point will be compared using a one sided test at the 5% level. Missing data will be excluded. The primary analysis will be performed for the ITT population.

The tests of the fixed effects will be presented, together with the estimated least squares means and summary statistics of the raw PaO2/FiO2 ratio for each of the two treatments at each time point. The estimated treatment difference between repertaxin and placebo at each time point will be presented together with the corresponding 95% confidence interval. The confidence interval will be generated using  $\alpha=0.10$  and the lower limit will be replaced by  $-\infty$ .

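### The sample size section assumes one primary comparison at 24 h, but the analysis tests 0 h and 24 h each at one-sided 5% with no order or success rule, so the 5% level holds only under a rule the plan does not state

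*SAP*

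**What the plan says.** - **Primary endpoint.** Protocol 4.2.1.1 defines it as the "ratio measured at FiO₂ = 1 during mechanical ventilation on ICU admission (time 0) and at 24 hours after ICU admission". SAP 4.1 has the "ratio measured at ICU admission (time 0) and 24 hours post ICU admission". Neither ranks one time above the other.
- **Tests.** Protocol 9.4.2 analyses the two times separately: "Treatment effect will be primarily compared using a one-sided 0.05 level test and then re-tested for consistency with a two-sided 0.05 level test". SAP 9.5.1, under Primary analysis: "The treatment effect within each time point will be compared using a one sided test at the 5% level".
- **Multiplicity.** SAP 9.5.1 holds that "adjustments for multiplicity are not considered necessary". It gives two reasons: the trial is not pivotal, and both contrasts come from a single repeated measurements model.
- **Sample size.** SAP 3.2 lists among its assumptions "One primary comparison: repertaxin versus placebo at 24 hours post ICU admission", with a type I error of 0.05. Protocol 9.1 gives the same power figures, "using a two group t-test with a 0.05 one-sided significance level", but does not name 24 h as the only comparison. It pairs the 24 h placebo mean (315 mmHg) with the SD from the initial ICU assessment (137 mmHg; the 24 h SD is 117).
- **Changes.** SAP 1.2 declares no change from the protocol.

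No section gives a test order, a split of alpha, or a rule on whether one or both times must be significant.

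**The concern.** The design section and the analysis section describe different trials. One has a single decisive test; the other has two tests of equal standing, each at the full 5%.

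The stated reason for not adjusting rests partly on fitting both times in one model. Such a model describes the within-patient correlation and so gives suitable standard errors. It does not limit the chance that at least one of two contrasts crosses its own 5% threshold.

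The risk is in how the result is read. With no success rule, significance at either time could be reported as a positive primary result, and the time point that carries the conclusion could be chosen after unblinding. One-sided 5% is already a lenient threshold for the decision on further development.

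**Working it through.** **1. The plan's own power.** Inputs from SAP 3.2 and Protocol 9.1: 50 per group, SD 137, one-sided 0.05, differences of 70 and 50 mmHg.

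SE of the difference = 137 × √(2/50) = 27.4. Standardised differences: 70/27.4 = 2.555 and 50/27.4 = 1.825. Normal approximation: Φ(2.555 − 1.645) and Φ(1.825 − 1.645).

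| Difference | Stated | Normal | Noncentral t, 98 df | Same, two-sided 0.05 |
|---|---|---|---|---|
| 70 mmHg | 81% | 81.9% | 81.4% | 71.6% |
| 50 mmHg | 56% | 57.1% | 56.7% | 43.9% |

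The stated figures are those of one test at one-sided 0.05.

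**2. Two tests, success at either.** With no effect at either time, the chance of at least one significant result is 1 − P(Z₁ < 1.645, Z₂ < 1.645), where Z₁ and Z₂ are bivariate normal with correlation ρ. At ρ = 0 this is 1 − 0.95² = 9.75%. The documents do not give ρ, so the other rows are assumptions.

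| ρ (assumed) | Chance of at least one false positive |
|---|---|
| 0 | 9.75% |
| 0.3 | 9.3% |
| 0.5 | 8.8% |
| 0.7 | 8.0% |
| 0.9 | 6.8% |

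The rate falls to 5% as ρ approaches 1. Simulated pairs of t-tests with 50 per arm gave 9.8%, 9.2%, 8.7% and 8.0% at ρ = 0, 0.3, 0.5 and 0.7.

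**3. Two tests, both required.** A false claim then needs the test of a true null to be significant, so the rate is at most 5% without adjustment. With no effect at either time and ρ = 0.5 it is 1.2%.

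**4. The model as listed.** SAP 9.5.1 names fixed effects for center, time point and treatment. The table shell in SAP 13 adds only center-by-treatment. Without a treatment-by-time term, the estimated treatment difference is the same at 0 h and 24 h, which makes one test at 5%. Yet the SAP asks for least squares means for each time-and-treatment combination, and the shell has a separate difference and p-value for each time. Separate contrasts are clearly intended, and the listed terms do not produce them.

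**5. Ways to hold 5%.**

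- *Fixed order, 24 h then 0 h, each at one-sided 5%.* If there is no effect at 24 h, any false claim first needs a significant 24 h test (5%). If there is an effect at 24 h but none at 0 h, it needs a significant 0 h test (5%). The rate is at most 5% either way, and 24 h power stays at 81.4% and 56.7%.
- *Bonferroni, one-sided 0.025 each.* The rate is 4.9% at ρ = 0 and 4.5% at ρ = 0.5. Power per time point falls to 71.6% and 43.9%, and about 62 per arm are needed to regain 81% at 70 mmHg.

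**The case against.** The strongest reply is that this is an open choice in a phase 2 trial. The SAP says first that the study is not pivotal, and Protocol 9.1 says that no data exist to estimate the effect size and that the trial would still provide useful data on it. Declining to adjust on that ground is defensible. That stands: it lowers the weight of the point. It does not say which comparison decides the trial, and the plan never states the error rate it accepts.

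There is also partial protection. The primary ITT analysis is repeated two-sided at 5%, which for benefit is one-sided 2.5% at each time, the Bonferroni level for two tests. Both contrasts appear side by side in the table shell. This helps a careful reader, but the repeat is listed as a sensitivity analysis and does not set the success criterion.

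It can also be said that SAP 3.2 is the outlier, since the protocol synopsis, Protocol 4.2.1.1 and 9.4.2 and SAP 4.1 all name both times. Correcting SAP 3.2 and stating a success rule would indeed remove the conflict too. Any remedy, though, has to state the rule that is now missing.

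A reader might go further and infer that the trial's type I error is 8–9%. The documents do not support that as a flat statement: they never say that a win at either time suffices, and they give no correlation. Calling the two times co-primary would not help, because that term usually means that both must succeed, in which case there is no inflation.

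**Conclusion.** The conflict between SAP 3.2 and the endpoint and analysis sections is certain from the text. So is the lack of an order or success rule, and the repeated measurements model does not fill that gap.

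The size is conditional. If a win at either time counts, the false-positive chance exceeds the stated 5%: at most 9.75% for non-negative correlation, and about 8–9% at an assumed correlation of 0.3 to 0.7. If both must succeed, it is at most 5%. The calculation assumes separate contrasts at the two times, which the SAP intends but its listed model terms do not deliver.

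The plan should be changed, though the disclosed non-pivotal status makes this a matter of clear inference and not a fatal flaw.

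**What to change.** Before database lock and unblinding:

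1. State a fixed order in SAP 9.5.1: the 24 h contrast first at one-sided 5%, matching SAP 3.2; the 0 h contrast at one-sided 5% only if 24 h is significant.
2. Add the treatment-by-time term to the model and to the table shell, so that the two contrasts exist.
3. Delete the claim that the repeated measurements model makes adjustment unnecessary.
4. Align SAP 4.1 and Protocol 4.2.1.1 and 9.4.2 with this order.

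The stated sample size and power are unchanged. The costs are:

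- An effect seen only at 0 h can no longer be claimed as a primary success.
- The protocol wording needs a signed amendment and IRB/REB handling under Protocol 12.5, with about 60 patients already randomized when the SAP was written.
- The decisive test rests on the time at which patients extubated before 24 h have no value and are left out of the primary analysis. The substitution analysis already planned in SAP 9.5.1 should be reported beside it. The 81% figure assumes 50 observed values per arm, as SAP 3.2 already does.

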#### Primary analysis

The ratio at the two time points will be analyzed using a repeated measurements model using PROC MIXED within SAS®. The model will include fixed effect terms for center, time point and treatment. Time point will be specified as a repeated measurement. In order to select an appropriate matrix for the observations within each patient, 3 models will be fitted using the compound symmetry, Huynh-Feldt and unstructured structures. The matrix for the final model will be selected using Akaike's Information Criterion where the lowest value indicates the best fit. Type III sums of squares from the mixed procedure within SAS® will be used to assess the significance of individual terms within the model using the selected matrix structure. The importance of the treatment-by-center interaction will be investigated but if the term is not significant at the 10% level, it will be excluded from subsequent models. If there are insufficient data within each center and treatment combination to allow estimation of effects, centers will be pooled based on similar surgical practices.

The adjusted least squares means will be estimated for each combination of time point and treatment. The treatment effect within each time point will be compared using a one sided test at the 5% level. Missing data will be excluded. The primary analysis will be performed for the ITT population.

The tests of the fixed effects will be presented, together with the estimated least squares means and summary statistics of the raw PaO2/FiO2 ratio for each of the two treatments at each time point. The estimated treatment difference between repertaxin and placebo at each time point will be presented together with the corresponding 95% confidence interval. The confidence interval will be generated using  $\alpha=0.10$  and the lower limit will be replaced by  $-\infty$ .

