Patients will be excluded if they are: recipients of an intended multiple organ transplant, including heart-lung and liver-lung transplantation; recipients of a lung from a living lobar donor or a lung from a non-heart beating donor; recipients of a re-do lung transplantation. Patients requiring mechanical ventilation at the time of transplant, or with extra-respiratory tract site of infection, or with hepatic dysfunction at the time of transplant, or with hypersensitivity to ibuprofen or to more than one NSAID, or to medications belonging to the class of sulfonamides will be excluded as well. Also, patients planned to receive Orthoclone OKT3 or Campath induction immunosuppression or planned to receive sirolimus in the first three months after transplantation, or simultaneously participating in any other studies involving a study drug to be administered concomitantly with the Investigational Product and/or a study drug intended to prevent ischemia/reperfusion injury will be excluded. Pregnant or breast feeding women will be excluded.

Investigational drug

Repertaxin: 33 mg/mL aqueous injectable solution of repertaxin (per single 10 mL ampoule).

Placebo: 9 mg/mL aqueous injectable solution of sodium chloride (NaCl) (per single 10 mL ampoule)

For each 24 hour administration period, a dosing solution will be prepared from the contents of 23 ampoules (230 mL), diluted with 370 mL of 0.9 % sterile saline.

The study drugs will be administered as a continuous i.v. infusion into a (high flow) central vein, by an infusion pump, starting approximately 2 hours before reperfusion of the (first) transplanted lung occurs. An initial 'loading dose' of repertaxin of 4.488 mg/kg body weight/hour will be administered over 30 min followed by a maintenance dose of 2.772 mg/kg body weight/hour lasting 47.5 hours. Placebo will be volume matched saline. Total infusion volume will not exceed 500 mL/24 hours.

Statistics

Data for the double-blind (main) phase of the study (up to 30 days post-treatment) will be presented in the clinical study report. Data collected during the open phase of the study (from 1 month up to 12 months) will be presented in an addendum to the clinical study report.

Appropriate descriptive statistics will be produced, according to the variable.

The primary endpoint will be analyzed by ANOVA and separate comparisons at two time points (0 hours on ICU admission and 24 hours after ICU admission).

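### The SAP replaces the protocol's separate primary ANOVAs with a joint repeated-measures model, declares no change from the protocol, and lists no treatment-by-time term in that model

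*SAP*

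**What the plan says.** **Protocol.** Section 9.4.2 says the ratio "will be analyzed separately, at the two time points: 0 hours (ICU admission) and 24 hours after ICU admission". On the model it says "Analysis of variance will be used, including terms for treatment and center", and on the test "Treatment effect will be primarily compared using a one-sided 0.05 level test". Missing data are excluded. The synopsis puts it more loosely: "The primary endpoint will be analyzed by ANOVA and separate comparisons at two time points".

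**SAP.** Section 9.5.1, under the heading Primary analysis, says the ratio at the two times "will be analyzed using a repeated measurements model using PROC MIXED". On its terms: "The model will include fixed effect terms for center, time point and treatment". On covariance: "3 models will be fitted using the compound symmetry, Huynh-Feldt and unstructured structures", with the lowest AIC deciding. On the test: "The treatment effect within each time point will be compared using a one sided test at the 5% level". Missing data are again excluded. The six presentations listed in 9.5.1, and Tables 2.1.1 to 2.1.6 in section 11, are all repeated-measurements analyses. The table shell in section 13 has rows for center, time, treatment and center-by-treatment, and none for treatment-by-time. Section 1.2, on changes from the protocol, records none. Section 1.1 says the plan was written from the protocol revision of 30 August 2005.

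**The concern.** Both documents use a one-sided 5% test, name ITT as the main population and exclude missing data. The disagreement is about the model, and it shows in two places.

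First, the two methods use different data. Blood gases are measured during ventilation and stop at extubation, and both documents provide for patients extubated before 24 h. Such a patient is absent from the 24 h ANOVA. In the joint model, if only the missing record is dropped, the 0 h value stays in and informs the 24 h contrast through the within-patient correlation.

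Second, without a treatment-by-time term the joint model has a single treatment parameter, so the same difference and p-value would be reported at 0 h and at 24 h.

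A borderline result could then be positive under one document and negative under the other. Because the change is undeclared, a reader holding the protocol could question which analysis was prespecified. The SAP also gives the joint model as part of its reason for not adjusting for two time points, and that reason has no counterpart in the protocol's analysis.

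**Working it through.** **1. The plan's own power figures.** Inputs from Protocol 9.1: 50 per group, SD 137 mmHg, one-sided 5% two-group t-test. Noncentrality = difference / (137 × √(2/50)) = difference / 27.4.
- 70 mmHg: 70/27.4 = 2.555, power 81.4% (stated 81%).
- 50 mmHg: 50/27.4 = 1.825, power 56.7% (stated 56%).

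The stated figures reproduce to within a percentage point. They describe a single-time-point test, which is closer to the protocol's ANOVA than to the joint model.

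**2. What the SAP's listed terms estimate.** Write the mean as center + time(t) + β × treatment. The treatment difference at 0 h is [time(0) + β] − time(0) = β. At 24 h it is also β.

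For an illustration, take the SDs in Protocol 9.1 (137 at 0 h, 117 at 24 h) and assume a correlation of 0.5.
- Variances are 137² = 18,769 and 117² = 13,689. The covariance is 0.5 × 137 × 117 = 8,014.5.
- With complete data and unstructured covariance, and ignoring center, the two times are weighted in the ratio (13,689 − 8,014.5) : (18,769 − 8,014.5) = 5,674.5 : 10,754.5. That is 0.345 : 0.655.
- A true effect of 0 at 0 h and 70 mmHg at 24 h would therefore be estimated as 0.655 × 70 ≈ 46 mmHg at both times.

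**3. How often the 24 h decisions differ.** Simulation, 2,000 trials per scenario: 100 patients, 8 centers (SAP 3.3), SDs 137 and 117, one-sided 5%. The protocol ANOVA is compared with the joint model, fitted with the SAP's listed terms and then with treatment-by-time added. Covariance is unstructured, by approximate iterated GLS rather than PROC MIXED itself.

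The documents give no correlation, no missing rate and no expected effect at 0 h, so all three are assumed. Missingness at 24 h follows a logistic model with intercept log(0.3/0.7) and slope 1 per SD of the 0 h ratio. The nominal 30% works out at about 33% missing with no 0 h effect, and 37-38% when treatment raises the 0 h ratio by 50-70 mmHg.

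| Corr. | Effect 0 h / 24 h | Nominal missing | Reject at 24 h: ANOVA | Listed terms | With treatment-by-time | Disagree: listed terms | Disagree: with treatment-by-time |
|---|---|---|---|---|---|---|---|
| 0.5 | 0 / 0 | 0% | 5.2% | 5.1% | 5.3% | 3.4% | 0.7% |
| 0.5 | 0 / 0 | 30% | 5.4% | 5.1% | 4.8% | 5.9% | 3.1% |
| 0.5 | 0 / 70 | 0% | 89.2% | 64.7% | 89.4% | 24.6% | 1.2% |
| 0.5 | 0 / 70 | 30% | 74.6% | 39.8% | 78.0% | 37.7% | 9.6% |
| 0.5 | 70 / 70 | 30% | 66.3% | 89.2% | 76.1% | 25.8% | 13.9% |
| 0.5 | 50 / 50 | 30% | 43.6% | 65.3% | 50.9% | 30.6% | 14.9% |
| 0.3 | 0 / 50 | 30% | 51.3% | 27.3% | 51.4% | 30.1% | 9.6% |
| 0.7 | 0 / 50 | 30% | 49.5% | 28.0% | 56.0% | 28.1% | 18.5% |

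A repeat simulation at correlation 0.5 gave 1-4% with complete data and the added term. With nominal 30% missing and a true effect it gave about 10-13% with the added term and 22-39% with the listed terms.

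**The case against.** **The SAP names its own primary analysis.** This stands. The section is headed as primary, ITT is named as the primary result, the SAP is to be finalized before lock, and unblinding follows lock. A reader might infer that two rival p-values will be reported at each time point, or that nothing says which result decides. The documents do not support that: the SAP plans one analysis and produces no ANOVA. What is missing is a declaration that the SAP departs from the protocol and takes precedence.

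**The change may look like a late, data-driven switch.** About 60 patients had been randomized when this SAP version was written, so a reader might infer this. The documents give no sign of it. SAP 1.3 shows that a previous SAP version already chose a covariance matrix by AIC, no efficacy interim is planned, and the blind holds until lock.

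**The protocol versions may differ.** This cannot be excluded, because the date of the protocol in hand is not visible. The two texts still need reconciling.

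**The synopsis is compatible with either method.** Largely true: its wording could fit one model with a contrast at each time. The clear conflict is with 9.4.2.

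**The treatment-by-time term was probably intended.** This is plausible, because the SAP asks for least squares means for each combination of time and treatment. But neither the list of terms nor the shell contains it.

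**The size depends on chosen inputs.** This stands too. With 70 mmHg at both times and treatment-by-time included, missingness unrelated to the 0 h ratio lowers disagreement from about 14% to 9%. If excluding missing data means dropping whole patients, which the SAP does not settle, it falls to about 4%.

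**Conclusion.** The conflict is real. Protocol 9.4.2 and SAP 9.5.1 specify different primary analyses, SAP 1.2 denies any change, and the joint model as listed cannot give a separate treatment comparison at each time.

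With treatment-by-time added and complete data, the 24 h decisions nearly coincide. With a true effect, correlation 0.5 and nominally 30% missing at 24 h, they differ in roughly 10-15% of trials with that term and 20-40% with the listed terms only. These figures rest on the assumed correlation, missingness and 0 h effect, and on dropping records rather than patients. Neither method dominates under the listed terms: power at 24 h falls if the effect is confined to 24 h and rises if it is present at both times.

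The per-test error rate is near 5% for both methods when there is no effect at either time, so this is not a finding of general type I inflation. The exception follows from the single β. If the effect exists only at 24 h, the listed-terms p-value would also be reported at 0 h, where it rejects in 64.7% of trials with complete data.

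**What to change.** Before the Month 1 lock and unblinding:

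1. In SAP 1.2, replace the statement of no changes with an entry declaring the move from separate ANOVAs to the repeated-measures model, and state that the SAP model is the deciding analysis.
2. Add treatment-by-time to the model in SAP 9.5.1 and to the table shell in section 13, so that each time point has its own contrast. Making the SAP model decisive without this term would leave the main defect in place.
3. Report the protocol's ANOVA at each time point (ITT, one-sided 5%) as a labelled, non-deciding sensitivity table beside Table 2.1.1.
4. Align Protocol 9.4.2 and the synopsis at the next amendment.

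The cost is SAP wording, one model term and one extra table, with no new data. The downside is a second, non-deciding p-value at each time point in the report.
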